Our project is a **24-month longitudinal randomized controlled trial that aims to investigate the myopia development after topical application of 0.01% atropine in children with either fast or slow myopia progression classified according to their initial electro-retinal responses. This will help elucidate the effectiveness of using low concentration atropine for myopia control in children with different myopia progression rates.** All of the participated children will be allocated into fast or slow myopia progression group in accordance with the electro-retinal activities as measured by our established protocol from my GRF 2013 study. This protocol also enables us to find out how the retinal electrophysiological changes under the atropine treatment over a 24-month period. The characteristics of these retinal activities will help us to understand the retinal contribution to myopia development in human eye. Furthermore, it will advance our clinical decision to prescribe an appropriate myopia control treatment and be beneficial for the design of a highly effective treatment protocol for myopia control.

Subjects

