Based on the study of ATOM2 (Chia et al., 2012), the mean myopia progression rate under 0.01% atropine was -0.49 ± 0.63 D and the mean myopia progression rate in control was -1.20 ± 0.69 D). Hence, 9 subjects should be required for this project to demonstrate the effect of atropine on myopia control (type I error of 5% and the power of 80%; effect size = 1.07, two-tailed; paired group; GPower 3.1). However, based on the mfERG data of our pilot study (Figure 1), the mean inner retinal responses from fast and slow myopia progression group are 67.04 ± 30.54 uV/deg² and 80.61 ± 27.24 uV/deg², therefore the proposed study requires 38 subjects (type I error of 5% and the power of 80%; effect size = 0.47, two-tailed; paired group; GPower 3.1). Assume that the dropout rate of this study throughout the 2-year period is around 5% (according to our preliminary result from my GRF 2013 study) and after consolidation of both analyses, at least 40 subjects aged from 8 to 9 years will be recruited. Children at this age range are believed to be the group with the highest chance of myopia progression. As this study is a randomized controlled trial with two arms, one is the treatment arm and the other one is placebo arm. We will recruit 80 subjects in this study. All of them will receive an ophthalmic assessment including history taking, preliminary tests, objective and subjective refraction, external and internal ocular health assessments. The subjects who meet the following criteria will be recruited to participate in this study. The subjects must have the refractive error between -0.5D and -1D in both eyes and with the best-corrected visual acuity of logMAR 0.00 or better, normal color vision and ocular health. Subjects with any ocular disease, systemic disease and current or history of epilepsy will be excluded from the study.

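### The atropine-placebo model omits the baseline retinal marker on which the trial is built, and no stratification by that marker is stated

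*Protocol*

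**What the plan says.** The Protocol's Summary presents central retinal electro-activity as an important indicator of predisposition to fast progression and makes it the organising factor of the trial. The project "aims to investigate the myopia development after topical application of 0.01% atropine in children with either fast or slow myopia progression classified" by their initial electro-retinal responses. Every child receives a class: "All of the participated children will be allocated into fast or slow myopia progression group in accordance with the electro-retinal activities". No cut-off for the class is given.

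The Subjects section describes allocation in one sentence: "As this study is a randomized controlled trial with two arms, one is the treatment arm and the other one is placebo arm". On size it says "We will recruit 80 subjects in this study", which doubles an earlier minimum ("at least 40 subjects aged from 8 to 9 years will be recruited") to serve two arms. Neither document gives an allocation ratio, sequence method, block scheme or stratification factor, or a number of children per class or per class-by-arm cell.

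The SAP (Statistical analysis) compares annualised change in SER and AL between arms with a univariate GLM that has two covariates, baseline SER and age. Ring 1 IC, the central inner retinal response, enters separate analyses: its relation to change in SER and AL, a moderator analysis by arm, comparisons of correlation coefficients, and an ROC analysis. The SAP's fast progressor is defined by observed progression of at least 1.0 D a year, so it is not the baseline mfERG class.

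**The concern.** A baseline variable that predicts the outcome can be balanced by stratified allocation, adjusted for in the analysis, or both. For the variable this trial singles out as prognostic, the documents state neither for the main arm comparison. If one arm happens to receive more children with a weak central response, part of the observed atropine-placebo difference reflects that, and the planned model does not take it out.

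The two listed covariates are unlikely to stand in for the marker. Eligibility confines both to narrow ranges: refractive error between -0.5 D and -1 D, and age 8 to 9 years. At stake is precision in the main contrast, from information the trial collects anyway.

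**Working it through.** **1. The plan's own figures.**
- Atropine against control: "the mean myopia progression rate under 0.01% atropine was -0.49 ± 0.63 D", against -1.20 ± 0.69 D in control. Difference 1.20 - 0.49 = 0.71 D; pooled SD = √((0.63² + 0.69²)/2) = √0.4365 = 0.66 D; effect size 0.71/0.66 = 1.07. A paired t-test with the stated settings ("type I error of 5% and the power of 80%; effect size = 1.07, two-tailed; paired group; GPower 3.1") gives n = 9 (power 0.802).
- mfERG response, fast against slow: (80.61 - 67.04)/√((30.54² + 27.24²)/2) = 13.57/28.94 = 0.47. The stated settings ("type I error of 5% and the power of 80%; effect size = 0.47, two-tailed; paired group; GPower 3.1") give n = 38 (power 0.805).
- 38/0.95 = 40, and 40 × 2 = 80.

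All four figures reproduce. None concerns balance of the marker between arms.

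**2. Assumptions, because the documents give no figure.**
- 40 fast and 40 slow children.
- 40:40 allocation, not stratified by class.
- A fast-slow gap in progression of 0.3 to 0.6 D, on the same time scale as the 0.71 D and its SDs. The Protocol does not state that time scale.

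**3. How often imbalance arises.** The number of fast children in the atropine arm is hypergeometric (80 children, 40 fast, 40 drawn). Mean 20; variance 40 × 0.5 × 0.5 × 40/79 = 5.06; SD 2.25.
- 16:24 or worse, either direction: 11.7%.
- 15:25 or worse: 4.4%.

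Under simple 1:1 randomisation without fixed arm totals, 16:24 or worse in a class of 40 occurs in 26.8% of trials.

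**4. What a 16:24 split does to the arm contrast.** The fast share is 24/40 = 60% in one arm and 16/40 = 40% in the other, a difference of 0.20.
- Shift = 0.20 × (0.3 to 0.6) = 0.06 to 0.12 D, which is 8% to 17% of 0.71 D.
- SE of the arm difference = 0.66 × √(2/40) = 0.148 D.
- Shift in SE units = 0.06/0.148 to 0.12/0.148, about 0.4 to 0.8.
- At one SD of imbalance the shares differ by 2 × 2.25/40 = 0.1125, and the shift is 0.03 to 0.07 D.

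**5. What adjustment could recover.** With a 50:50 class, a gap g contributes g²/4 to the outcome variance: 0.0225 to 0.09 of 0.4365, or 5% to 21%. Removing it takes the SE from 0.148 D to √(0.414 × 2/40) = 0.144 D at the low end and √(0.3465 × 2/40) = 0.132 D at the high end. This supposes that the quoted SDs include the class variation and that baseline SER and age explain none of it.

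**6. Cost within class.**
- Efficiency of 16:24 against 20:20 = (2/20)/(1/16 + 1/24) = 0.96.
- Power for 0.71 D within a class of 40: 91.2% at 20:20 and 90.1% at 24:16.
- Treatment-by-class difference detectable with 80% power: 0.83 D at 20 per cell and 0.85 D with opposite 24:16 splits.
- If only 25 of the 80 are fast (assumed), 8:17 or worse occurs in about 5% of trials. The variance ratio is (1/8 + 1/17)/(2/12.5) = 1.15, about 7% on the SE.

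Steps 4 and 5 concern SER. The documents give no planning figures for AL.

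**The case against.** Three points on the other side have force.

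First, a reader might infer that randomisation was not stratified by class. The documents do not support that. The posted Protocol is a Summary and a Subjects section, and it is silent on the method. Silence shows only that stratification is not stated.

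Second, a reader might infer that imbalance within class distorts the fast-slow comparison, or that the drug-by-class question turns on the smaller class. Neither follows. Randomisation stays valid within each class, so unequal numbers leave the within-class effects unbiased, and the loss of precision is small. The SAP also never uses the binary class: it addresses the drug-by-retina question with continuous Ring 1 IC in the moderator analysis, so cell counts by class enter no planned model.

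Third, the shift in the arm contrast is chance imbalance. The ordinary standard error already allows for it, and type I error is not inflated. A 16:24 split is an uncommon event under fixed 40:40 totals, and the 0.06 to 0.12 D rests on an assumed gap.

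All three limit the point. They do not remove it. The moderator analysis is separate from the atropine-placebo comparison, which still omits the marker and so carries avoidable variance.

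**Conclusion.** The point holds as one of precision in the main arm comparison. The Protocol gives the baseline central inner retinal response prognostic importance, no stratification by it is stated, and the SAP's arm model does not adjust for it. An unlucky but plausible split (16:24 or worse, about 12% of trials) would move the unadjusted SER difference by 0.06 to 0.12 D or more, against an SE of about 0.148 D. On average, adjustment might lower that SE to between 0.144 and 0.132 D. These sizes depend on an equal class split, 40:40 allocation and a fast-slow gap of 0.3 to 0.6 D, none of which the documents give. The pilot effect size of 0.47 is for the mfERG response, so it does not fix the gap in progression. The improvement is modest and inexpensive. The documents do not support a claim of bias or of a faulty randomisation.

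**What to change.** Add baseline Ring 1 IC as a covariate, with baseline SER and age, in the GLM that compares annualised change in SER and AL between atropine and placebo. The measurement is already collected, and a continuous covariate needs no class cut-off. With 80 children, residual degrees of freedom go from 80 - 4 = 76 to 75. Any child without a usable baseline mfERG would need a stated rule.

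The SAP is written in the past tense and reports distribution checks. If the arm results have been seen, give the Protocol's prognostic rationale for the covariate and report the adjusted model beside the one with SER and age alone.

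State the randomisation method and whether it was stratified by mfERG class. If allocation were still open and a class cut-off were fixed beforehand, randomising in blocks within class would also be reasonable. It would cost a second list and a wait for the mfERG reading before each child is allocated.

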Title of Project: Tropical application of low-concentration (0.01%) atropine on the human eye with fast and slow myopia progression rate

NCT03374306

Date: 1 Jan 2018

Statistical analysis

Due to COVID-19-dependent closure of the university campus, the eye examinations were not always performed within the study-defined time window and were in-part delayed. To minimize the effect of delayed visits, change from baseline in SER and AL were normalized for time and expressed as annualized change for each participant. All participants included in the analysis had completed the baseline eye examination and at least 2 visits of follow-up eye examinations during the study period.

The data distribution was approximately normal (Shapiro-Wilk test – SER: $p = 0.16$; AL: $p = 0.27$). A univariate general linear model (GLM) was used to compare annualized change in SER and AL between the treatment groups (atropine vs. placebo), controlling for the baseline SER and age as covariates. Since a weakened central inner retinal response was reported as a risk factor for myopia development, the relationship between Ring 1 IC and annualized change in SER and AL were evaluated using GLM, and compared between the atropine and the placebo groups using moderator analysis. The correlation coefficients (R_p vs. R_a) were also compared between treatment types using Fisher's R-to-Z test in the Ring 1 IC, as well as other regions and MOFO mfERG parameters. All statistical procedures were performed with SPSS22.0 (IBM, Armonk, NY). Hochberg's adjustment was applied for multiple comparisons, with significance level set at $p \leq 0.05$. A receiver operating characteristics analysis was also performed to evaluate the predictive value of baseline Ring 1 IC on fast progressor (annualized progression ≥ 1.0 D) in each of the atropine and control group.

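### Baseline SER and age are stated as covariates only for the randomised treatment comparison, not for the Ring 1 IC analyses, where confounding is possible

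*SAP*

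**What the plan says.** For the comparison of arms, the SAP's Statistical analysis section specifies a univariate GLM on annualized change in SER and AL, "controlling for the baseline SER and age as covariates". The next sentence turns to the marker: "the relationship between Ring 1 IC and annualized change in SER and AL were evaluated using GLM", and this relationship was "compared between the atropine and the placebo groups using moderator analysis". Neither step names a covariate, and nothing says whether those of the treatment model carry over.

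The correlations R_p and R_a "were also compared between treatment types using Fisher's R-to-Z test in the Ring 1 IC" and for other retinal regions and mfERG parameters; partial correlations are not mentioned. The ROC is meant to "evaluate the predictive value of baseline Ring 1 IC on fast progressor", separately in each arm, with no age or SER term and no comparator model. The SAP adds that "Hochberg's adjustment was applied for multiple comparisons", which deals with multiplicity and not with confounding.

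The protocol's Subjects section restricts entry to ages 8 to 9 and refraction from -0.5 D to -1 D. It gives no adjustment rule.

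**The concern.** The stated covariates sit where they are needed least. Treatment is randomised, so baseline SER and age serve only precision in that comparison. Ring 1 IC is a trait the child brings to the trial, and randomisation does not balance age or starting refraction across its levels. If younger children both progress faster and have a different central inner retinal response, an unadjusted Ring 1 IC slope will carry part of the age effect.

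The claims affected are central. The protocol's Summary presents central retinal activity as a marker of predisposed risk, classifies children by it, and hopes to guide prescribing with it. A marker that stands in for age would not support that use as an independent retinal risk, nor would a moderator finding that really belongs to age.

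**Working it through.** **Sample size.** The protocol's retinal means and SDs (67.04, SD 30.54; 80.61, SD 27.24) give d = 13.57 / sqrt((30.54² + 27.24²)/2) = 0.469, matching its stated 0.47. Under its stated settings ("type I error of 5% and the power of 80%; effect size = 0.47, two-tailed; paired group; GPower 3.1"), exact noncentral-t power gives n = 38, and 38/0.95 = 40. Both figures reproduce. With 80 recruited and 5% dropout, 80 × 0.95 = 76 remain. I take 38 per arm; the allocation ratio is not stated, so this is an assumption. The SAP gives no figure for the Ring 1 IC analyses.

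**Association model.** Suppose Ring 1 IC has no effect of its own, and one covariate correlates a with Ring 1 IC and b with progression. The induced correlation is r = a × b. The chance of two-sided p < 0.05 is approximately P(Z > 1.96 − k) + P(Z < −1.96 − k), with k = atanh(r) × sqrt(n − 3). No document gives a or b, so both are assumptions.

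| b (progression) | a (Ring 1 IC) | r | k at n = 76 | False-positive rate |
|---|---|---|---|---|
| 0.2 | 0.2 | 0.04 | 0.34 | 6% |
| 0.2 | 0.3 | 0.06 | 0.51 | 8% |
| 0.3 | 0.3 | 0.09 | 0.77 | 12% |
| 0.35 | 0.4 | 0.14 | 1.20 | 23% |

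Simulation at n = 76 (20,000 runs) gives 8.0% for the second row and 22.6% for the last. With the covariate in the model the rate returns to about 5%. Within one arm (n = 38) the third row falls to 8%.

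**How plausible are such correlations under the entry limits?** If age is uniform from 8 to under 10, its SD is 2/sqrt(12) = 0.58 years. If baseline SER is uniform over 0.5 D, its SD is 0.5/sqrt(12) = 0.14 D. Take the SD of annualized progression as 0.35 D, about half of the protocol's quoted 0.63 to 0.69 D read as two-year values (an assumption). The slope needed for b = 0.3 is then:
- age: 0.3 × 0.35/0.577 = 0.18 D/yr per year of age;
- baseline SER: 0.3 × 0.35/0.144 = 0.73 D/yr per dioptre.

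If the quoted SDs are annual, these slopes roughly double. Age is the more plausible confounder.

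**Moderator model.** Simulations used 38 per arm and no true Ring 1 IC effect.
- Covariate with the same effect in both arms (b = 0.35, a = 0.4): the unadjusted treatment × Ring 1 IC test rejects 5.0%. There is no distortion.
- Covariate acting in placebo only (b = 0.4 against 0, a = 0.4): 10.7% unadjusted, 10.8% with the covariate main effect added, and 5.3% once covariate × treatment is also included.
- Fisher's R-to-Z behaves alike: about 5% when the effect is equal by arm, and 9% to 20% when b is 0.5 in placebo and 0 in atropine with a = 0.3 to 0.5.

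**Price of partial correlations.** Conditioning on two covariates changes the Fisher variance from 1/(n − 3) to 1/(n − 5). At 38 per arm the SE of the difference goes from sqrt(2/35) = 0.239 to sqrt(2/33) = 0.246, about 3% more.

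**The case against.** The other side has five arguments, and most limit the point without removing it.

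- **Silence is not absence.** A reader might infer that the Ring 1 IC GLM and moderator model were run unadjusted. The SAP does not say so. It has just defined a GLM with covariates and leaves open whether they carry over. Only the R_p versus R_a comparison and the ROC are described in a form that implies no covariates. This stands.
- **Moderation.** A reader might infer that any prognostic covariate linked to Ring 1 IC creates false moderation. Under randomisation it does not, unless its effect differs by arm. This stands, and it changes the remedy: adding baseline SER and age as main effects leaves the error where it was.
- **Treatment term.** A reader might infer that the Ring 1 IC GLM pools both arms with no treatment term. The same sentence goes on to a moderator analysis by arm, so the text does not clearly describe such a model. No loss of precision should be claimed on that basis.
- **AUC.** A reader might infer that an unadjusted AUC is an error. It is a valid measure of the marker's own predictive value, which is the stated aim. What it cannot show is added value over age and starting refraction.
- **Size.** Every correlation used here is assumed, and the narrow entry limits restrict both covariates. This stands as a limit on magnitude. It is no reason to leave out two variables that the SAP already uses in the treatment model.

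**Conclusion.** The point holds in a limited form. The covariates of the Ring 1 IC GLM and moderator model are unspecified, and those of the correlation comparison and ROC appear to be none. The risk of bias lies mainly in the association with progression. The 8% to 23% range rests on no true marker effect, normal variables, one confounder and the assumed correlations. Weaker correlations, such as 0.2 with each, bring the rate down to 6%, and the documents cannot fix the true value. For moderation the risk is conditional on an arm-specific covariate effect: about 11% against 5% in the scenario examined, and nil if the effect is equal by arm. The AUC needs a companion analysis and not a replacement. This should be changed, because the adjustment removes a possible explanation for a central claim at almost no cost.

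**What to change.** State the covariates for each Ring 1 IC analysis:

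- **Association GLM:** treatment, Ring 1 IC, baseline SER and age.
- **Primary moderator model:** treatment, Ring 1 IC, treatment × Ring 1 IC, baseline SER, age, treatment × baseline SER and treatment × age. The covariate interactions belong in this model, not in a sensitivity run.
- **R_p versus R_a:** within-arm partial correlations given baseline SER and age, with Fisher variance 1/(n − 5). Apply the same to the comparisons described as "in the Ring 1 IC, as well as other regions and MOFO mfERG parameters".
- **ROC:** keep the unadjusted AUC in each arm, and also report the AUC of age plus baseline SER with and without Ring 1 IC.

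Base any statement of independent retinal risk or moderation on the adjusted results.

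The cost is SAP wording and a rerun on data already held. The added terms take two degrees of freedom in the association model (residual 73 to 71 at n = 76, counting treatment in both) and four in the moderator model (72 to 68). The reported Ring 1 IC association may become slightly weaker.

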Title of project:

Tropical application of low-concentration (0.01%) atropine on the human eye with fast and slow myopia progression rate

Summary

NCT03374306

Date: 1 Jan 2018

Myopia (short-sightedness) has been an epidemic worldwide. In Hong Kong, the prevalence of myopia is approximately 80% at the end of childhood, and the rate of myopia progression among children varies. **Tropical application of 0.01% atropine is a newly recommended pharmacological myopia control treatment.** Recent studies reported that it is effective to slow down myopia progression. **The findings from my GRF 2013 study showed that young children with an initial weakened central electrical signal from the inner retina had faster myopia progression. This indicates that the central retinal electro-activity is an important indicator to find out the predisposed risk of fast myopia progression.** Since the electro-retinal activities measured by my new protocol can classify the children into fast or slow myopia progression group, we speculate that studying the effect of atropine on these two groups will help us better understand the effectiveness of the drug in myopia control for the children with different predisposed risks.

There has been no study investigating the treatment effect of atropine on the children with either fast or slow myopia progression rate, neither has there been clinical finding to demonstrate whether the children with either fast or slow myopia progression will show the same treatment effect of atropine. Hence, longitudinally studying the underlying retinal activities that regulate the control of myopia progression using atropine in these two group of children will help evaluate the clinical effectiveness and improve the clinical judgement in prescribing this treatment.

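### For mfERG measures other than Ring 1 IC, the only between-arm comparison named is Fisher's R-to-Z, an indirect guide to whether atropine's effect depends on the measure

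*SAP*

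**What the plan says.** The SAP's Statistical analysis section sets out these analyses:

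- **Treatment comparison.** A GLM compares annualised change in SER and AL between arms, "controlling for the baseline SER and age as covariates". It contains no mfERG term.
- **Ring 1 IC.** Its relationship with annualised change is fitted by GLM and "compared between the atropine and the placebo groups using moderator analysis". No other measure is named in that sentence.
- **Correlations.** R_p and R_a are compared by Fisher's "R-to-Z test in the Ring 1 IC, as well as other regions and MOFO mfERG parameters". No covariates are named for this step.
- **ROC.** This covers baseline Ring 1 IC only, separately within each arm, so it is not a between-arm comparison.
- **Multiplicity.** Hochberg's adjustment is applied at 0.05. The tests that make up the family are not listed.

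The protocol's Summary gives the motivating question: it is not known "whether the children with either fast or slow myopia progression will show the same treatment effect of atropine".

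**The concern.** The protocol's question concerns a difference in treatment effect across levels of a retinal measure. In a regression of progression on that measure, this is a difference between the arms' slopes, that is, a treatment × measure interaction. The SAP provides such a test for Ring 1 IC and names none for the other regions and MOFO parameters.

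Fisher's R-to-Z compares correlations instead. Within an arm, r = slope × SD(measure) / SD(progression). Randomisation makes the spread of a baseline measure equal in expectation. It does not do so for the spread of progression, which treatment can change. Equal slopes can therefore give unequal correlations, and unequal slopes can give equal ones.

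At stake is how secondary results are read. A significant difference between R_p and R_a in some region might be reported as atropine working differently according to that response, and a null result as showing that it does not. The atropine-placebo comparison and the Ring 1 IC moderator analysis are unaffected.

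**Working it through.** **Inputs from the protocol (Subjects).** Atropine: "mean myopia progression rate under 0.01% atropine was -0.49 ± 0.63 D". Control: "mean myopia progression rate in control was -1.20 ± 0.69 D". Recruitment is 80 in two arms, with about 5% dropout. Taking equal arms, 80/2 = 40 and 40 × 0.95 = 38 per arm.

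**Assumed, because the documents give no values.** Placebo r of 0.3 to 0.7; the same distribution of the measure in both arms; normal data; no covariates; single two-sided 5% tests before Hochberg.

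**The plan's own figures.** The plan gives no size or power for the R-to-Z comparison. Its stated sample sizes reproduce by exact paired t-test (effect size 1.07 gives 9; 0.47 gives 38; 38/0.95 = 40), but this point does not depend on them.

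**Step 1: Fisher's test when the slopes are equal.** With a common slope and measure SD, r_a = r_p × 0.69/0.63 = 1.095 × r_p. The SE of the difference in Fisher z is √(1/35 + 1/35) = 0.239. The shift is δ = [atanh(r_a) − atanh(r_p)] / 0.239, and the rejection rate is Φ(−1.96 + δ) + Φ(−1.96 − δ).

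At r_p = 0.5: r_a = 0.548, δ = (0.6150 − 0.5493)/0.239 = 0.275, rate 5.9%. At r_p = 0.7: r_a = 0.767, δ = (1.0122 − 0.8673)/0.239 = 0.606, rate 9.3%.

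Simulation (100,000 trials per scenario; the interaction test is the OLS slope difference with pooled residual variance, 72 df) agrees:

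| Placebo r (assumed) | 0.3 | 0.4 | 0.5 | 0.6 | 0.7 |
|---|---|---|---|---|---|
| Implied atropine r | 0.33 | 0.44 | 0.55 | 0.66 | 0.77 |
| Fisher rejects, % | 5.1 | 5.4 | 5.9 | 6.9 | 9.3 |
| Interaction rejects, % | 5.0 | 5.0 | 4.9 | 5.2 | 4.9 |
| Tests disagree, SDs 0.69 and 0.63, % | 3.2 | 4.3 | 5.6 | 7.6 | 10.7 |
| Tests disagree, equal SDs, % | 2.8 | 3.7 | 4.7 | 5.5 | 6.5 |

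Much of the disagreement is present even with equal SDs. The SD difference adds between 0.4 points (r = 0.3) and 4.2 points (r = 0.7).

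**Step 2: how unequal the spreads must be.** For Fisher's test to reach 10% under equal slopes, the atropine/placebo SD ratio must fall to 0.69, 0.77, 0.82, 0.87 and 0.91 at r = 0.3, 0.4, 0.5, 0.6 and 0.7. The protocol's ratio is 0.63/0.69 = 0.91, so it comes near this only at r = 0.7.

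**Step 3: power when the slopes differ (same SDs; the slope changes are assumed).**

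| Placebo r | 0.3 | 0.5 | 0.7 |
|---|---|---|---|
| Atropine slope halved: interaction, % | 10.3 | 22.3 | 46.4 |
| Atropine slope halved: Fisher, % | 9.2 | 20.5 | 49.7 |
| Atropine slope zero: interaction, % | 26.8 | 64.6 | 93.8 |
| Atropine slope zero: Fisher, % | 25.8 | 64.4 | 95.6 |

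**Step 4: the opposite failure.** Suppose atropine shrank slope and residual spread together by 0.49/1.20 = 0.41. The correlations would then be equal. At r = 0.5 and 38 per arm, in 20,000 runs, Fisher rejects 5.2% and the interaction test 46.5%. This shows the direction of the error only: a spread ratio of 0.41 is far from the protocol's 0.91.

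The documents give no SD for axial length, so AL is not quantified.

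**The case against.** The case for leaving the SAP alone has four parts.

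1. **The SAP makes no claim about what R-to-Z shows.** It says only that the correlations were compared. This stands: the point is a gap in the named analyses and a caution on interpretation, not a stated error.
2. **The trial's main hypothesis already has its interaction test.** Both documents tie risk of fast progression to the central retinal response, and the SAP names a moderator analysis for Ring 1 IC. No effect-modification hypothesis is stated for other regions. This stands as a limit on importance, and it is why the added models should be labelled exploratory.
3. **The two tests behave much alike on the protocol's SDs.** This also stands. A reader might infer that an R-to-Z result says nothing about effect modification, or that it is badly prone to false positives. The documents support neither inference: type I error is near nominal up to r = 0.6, and power is similar throughout.
4. **The true correlations may be at or below the low end of the assumed range.** The protocol's pilot effect size of 0.47 converts to a point-biserial r of 0.47/√(0.47² + 4) = 0.23, or a biserial r of 0.23 × 0.5/0.399 = 0.29. This assumes equal fast and slow groups split at the median, which the protocol does not state. At those values Fisher rejects 5.1% and 5.3% under equal slopes, so the distortion is negligible. Interaction power for a halved slope is only 8% and 10%. This is a rough guide, not an arm-specific correlation from this trial.

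What remains is that the slope difference answers the protocol's question directly and on a clinical scale. The SAP already uses that approach for Ring 1 IC, and extending it costs almost nothing.

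**Conclusion.** The point holds as a minor one, an optional improvement. For the measures other than Ring 1 IC, the SAP names a comparison of strength of association and no direct test of effect modification.

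On the protocol's planning SDs, using R-to-Z as a stand-in costs little: about 5 to 7% rejection under equal slopes for placebo r of 0.3 to 0.6, about 9% at 0.7, and similar power. A larger discrepancy needs spreads of progression that differ more between arms than the documents show. The trial's own SDs are not given.

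The textual reading and the algebra are firm. The size rests on assumed correlations, cited planning SDs, equal arms of 38 and unadjusted single tests.

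**What to change.** For each mfERG measure other than Ring 1 IC, extend the moderator model: annualised change on treatment, measure, treatment × measure, baseline SER and age. The SAP names those two covariates for the treatment GLM and does not say whether the Ring 1 IC moderator model uses them, so state the covariates of each model.

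Report the slope in each arm and the slope difference, with confidence intervals. Apply Hochberg across these exploratory interaction tests only. Leave the Ring 1 IC moderator analysis outside that family and unchanged, so that the hypothesis-driven test is not pooled with exploratory ones. Keep R_p and R_a as descriptive measures of association.

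Label the added tests post hoc: the SAP already reports results ("The data distribution was approximately normal", with p-values), so prespecification cannot be restored.

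The cost is a few model runs on existing data, with no extra participants or measurements. Power is low, at about 10, 22 and 46% per single test for a halved slope at placebo r of 0.3, 0.5 and 0.7, and lower after Hochberg. A null result should be read from its confidence interval, not as proof of no modification.
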